### **7.2.5 Safety analyses**

Adverse events will be coded using the Medical Dictionary for Drug Regulatory Activities (MedDRA). Standard BI summary tables and listings will be produced. All adverse events with an onset between start of treatment and end of the residual effect period (REP), a period of 7 days after the last dose of trial medication, will be assigned to the on-treatment period for evaluation.

All treated patients will be included in the safety analysis. In general, safety analyses will be descriptive in nature and will be based on BI standards. No hypothesis testing is planned.

Statistical analysis and reporting of adverse events will concentrate on treatment-emergent adverse events, i.e. all adverse events occurring between start of treatment and end of the residual effect period. Adverse events that start before first drug intake and deteriorate under treatment will also be considered as 'treatment-emergent'.

Frequency, severity, and causal relationship of adverse events will be tabulated by system organ class and preferred term after coding according to the current version of the Medical Dictionary for Drug Regulatory Activities (MedDRA) at the database lock.

Laboratory data will be analysed both quantitatively as well as qualitatively. The latter will be done via comparison of laboratory data to their reference ranges. Values outside the reference range as well as values defined as clinically relevant will be summarised. Treatment groups will be compared descriptively with regard to distribution parameters as well as with regard to frequency and percentage of patients with abnormal values or clinically relevant abnormal values.

Vital signs, physical examinations, or other safety-relevant data observed at screening, baseline, during the course of the trial and at the end-of-trial evaluation will be assessed with regard to possible changes compared to findings before start of treatment.

Reasons for discontinuation and use of post-baseline concomitant medications will be tabulated.

The details of the analysis will be specified in the TSAP.

#### **7.2.6      Interim Analyses**

No interim analysis is planned but a Data Monitoring Committee (DMC) will be in place with tasks as described in [Section 8.7](#).

### **7.3            HANDLING OF MISSING DATA**

Missing data for KCCQ-TSS and NT-proBNP will be estimated using multiple imputation, according to whether patients are on-treatment or off-treatment.

Further details on multiple imputation and rules for handling missing data for other secondary and further endpoints will be specified in the TSAP.

### **7.4            RANDOMISATION**

The trial will be performed as a double-blind design with respect to placebo and empagliflozin. Patients will be randomised to the trial treatments in a 1:1 ratio. Patients will be stratified by HF status (de novo or decompensated chronic HF).

Patients will be randomised in blocks to double-blind treatment via an IRT system.

Approximately equal numbers of patients will be randomised to each treatment group.

BI will arrange for the randomisation and the packaging and labelling of trial medication. The randomisation list will be generated using a validated system, which involves a pseudo-random number generator so that the resulting treatment will be both reproducible and non-predictable. The block size will be documented in the Clinical Trial Report. Access to the codes will be controlled and documented.

### **7.5            DETERMINATION OF SAMPLE SIZE**

Powers for superiority in were estimated by simulation using a shared frailty approach. Initially a frailty value was simulated for each patient using a gamma distribution. Deaths were assumed to have constant hazard for any given patient dependent upon the frailty term, leading to a marginal Lomax distribution. HFEs were assumed to have a Poisson distribution within patients, again depending on the frailty parameter, leading to a marginal negative binomial distribution. The number of HFEs per patient was nominally capped at 7 per patient over the 90 day period. For KCCQ-TSS, the frailty terms were directly transformed into a capped normal distribution (values below 0 or above 100 set to 0 and 100 respectively). High frailties corresponded to low KCCQ-TSS scores and vice versa. The use of a shared frailty

parameter ensures correlation between components of the primary endpoint so that patients with poor outcomes in one component are also more likely to have a poor outcome in the others. Ten thousand simulations were used for each scenario. Calculations of the win ratio were performed using the generalised pairwise comparisons method from [Section 7.2.2](#). Simulations and calculations were performed using R statistical software Version 3.5.1.

A sample size of 500 randomised patients in total (250 per treatment group) would provide 87.4% power to detect a difference between the empagliflozin treatment group and placebo treatment group, in the win ratio, at a one-sided significance level of 0.025, assuming the following:

Proportion of patients who die within 90 days = 5% [[R19-2932](#)]

Hazard ratio for death component = 0.8 [[P15-09840](#)]

Proportion of patients with at least one HFE within 90 days = 15% [[R19-2932](#)]

Hazard ratio for HFE component = 0.7 [[P15-09840](#)]

KCCQ-TSS placebo mean = 55 [[R17-3082](#)]

KCCQ-TSS baseline adjusted standard deviation = 20 [[R17-3097](#)]

KCCQ-TSS treatment effect = 6 [[R19-3124](#)]

KCCQ-TSS win threshold = 5 [[R17-2687](#)]

Table 7.5: 1

Power estimates for various combinations of KCCQ-TSS treatment effects and death/HFE hazard ratios with 500 patients in total

HR for death	HR for HFE	KCCQ-TSS treatment effect			
		4	5	6	7
0.7	0.7	66.9%	80.1%	89.4%	94.7%
0.8	0.7	63.6%	77.2%	87.4%	93.4%
0.8	0.8	54.6%	68.8%	81.3%	89.7%

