### 3.3.4.1 Discontinuation of trial treatment

An individual patient will discontinue trial treatment if:

- The patient wants to discontinue trial treatment, without the need to justify the decision.
- The patient has repeatedly shown to be non-compliant with important trial procedures and, in the opinion of both, the investigator and sponsor representative, is not willing or able to adhere to the trial requirements in the future.
- The patient needs to take concomitant medication that interferes with the investigational medicinal product (see [Section 4.2.2.1](#)) for restricted medication
- The patient can no longer receive trial treatment for medical reasons (such as surgery, adverse events, other diseases, or pregnancy). In case of a temporary reason for treatment discontinuation, trial treatment should be restarted if medically justified, please see [Section 4.1.4](#).

Given the patient's agreement, the patient will undergo the procedures for the Early Discontinuation Visit as soon as possible after treatment discontinuation and the Follow-up Visit as outlined in the [Flow Chart](#) and [Section 6.2.3](#).

In addition, if the patient discontinues early, every effort should be made for the patient to attend the regularly scheduled study visits and have all study procedures performed except those pertaining to drug intake. However if this is not possible, then the remaining visits should be conducted by phone. In the rare case that even this is not possible, at least vital status and information about HFEs should be retrieved and documented at the day of the scheduled Visit 5 (Day 90).

If a patient becomes pregnant during the trial, the trial medication will be stopped, the patient will be followed up during the trial and until birth or termination of the pregnancy (see further details in Section 5.2.7.2).

If new efficacy/safety information becomes available, Boehringer Ingelheim will review the benefit-risk-assessment and, if needed, pause or discontinue the trial treatment for all patients or take any other appropriate action to guarantee the safety of the trial patients.

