### **7.2 PLANNED ANALYSES**

#### **7.2.1 General considerations**

The efficacy analysis will be based on the randomised set (RS), including all randomised patients. Analyses will be performed according to the intention-to-treat principle, with the use of all available data (on and off-treatment) through the trial period. This equates to a treatment-policy style estimand.

If a Per Protocol Set (PPS) is required, this will also be specified in the TSAP. Important protocol deviations will be described in the TSAP.

The safety analysis will be based on the treated set (TS), which consists of all patients treated with at least one dose of trial medication.

For both efficacy and safety analyses, treatment will be evaluated as randomised.

For all endpoints, baseline will be defined as the last available measurement before start of trial medication.

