## **7.2.2 Primary endpoint analyses**

The primary endpoint is clinical benefit, a composite of death, number of HFEs, time to first HFE and change from baseline in KCCQ-TSS after 90 days of treatment. This will be assessed using a win ratio approach.

All patients randomised to empagliflozin are compared to all patients randomised to placebo within their stratum.

For any two patients, a patient will win, i.e. achieve a better clinical outcome, as determined by assessing the following criteria sequentially, stopping when an advantage for either patient is shown:

1. Death within common follow-up time
  - death is worse than no death
  - earlier death is worse
  - tied, if not possible to determine
2. Number of HFEs within common follow-up time
  - more HFEs is worse
  - tied, if same number of HFEs
3. Time to first HFE within common follow-up time
  - earlier HFE is worse
  - tied, if not possible to determine
4. KCCQ-TSS change from baseline at Day 90
  - more positive change from baseline is better
  - the threshold for the difference is  $\geq 5$  for a win
  - tied, if difference  $< 5$

Note, priority is therefore given to death over HFE, and both of these over changes in KCCQ-TSS. Below are some examples:

1. Death, e.g.:
  - Patient A dies 30 days after randomisation (loses)
  - Patient B dies 40 days after randomisation (wins)
2. If no winner based on death, number of HFEs within common follow-up time, e.g.:
  - Patient A had two HFEs (loses)
  - Patient B had one HFE (wins)
3. If no winner based on number of HFEs, time to first HFE, e.g.:
  - Patient A had an HFE 30 days after randomisation (loses)
  - Patient B had an HFE 50 days after randomisation (wins)

Proprietary confidential information © 2020 Boehringer Ingelheim International GmbH or one or more of its affiliated companies

4. If no winner based on time to first HFE, KCCQ-TSS change from baseline at Day 90, e.g.:

- Patient A: KCCQ-TSS change from baseline at Day 90 is 5 (loses)
- Patient B: KCCQ-TSS change from baseline at Day 90 is 11 (wins)

The implemented generalised pairwise comparisons approach compares all patients in one treatment group to all other patients within their strata in the other treatment group. The win ratio is then calculated as the total number of wins in the empagliflozin group ( $N_w$ ) across all strata divided by the total number of losses ( $N_L$ ). So the win ratio is  $= N_w / N_L$ .

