### 7.2.3 Secondary endpoint analyses

Secondary endpoints will not be tested in a hierarchical sequence, and no adjustment for multiple comparisons is planned.

Change from baseline in continuous endpoints, such as KCCQ-TSS, will be analysed using restricted maximum likelihood estimation based on a mixed-effect model for repeated measures (MMRM) analysis to obtain adjusted means for the treatment effects. This model will include discrete fixed effects for treatment group (empagliflozin or placebo) and HF status (de novo or decompensated chronic HF) at each visit and continuous fixed effects for baseline value at each visit. Missing data caused by patient withdrawal or other reasons will be handled implicitly by the MMRM approach.

[figure not shown]
Area under the curve (AUC) of change from baseline in log-transformed NT-proBNP level over 30 days of treatment will be analysed by an analysis of covariance (ANCOVA). Based on literature reviews, NT-proBNP level is regarded as log-normally distributed, therefore values will be log-transformed prior to analysis [[R19-3044](#)]. The linear trapezoidal rule will be used to calculate the AUC after the log-transformation has been applied to each value. Analysis of covariance (ANCOVA) with a discrete fixed effect for HF status (de novo or decompensated chronic HF) and a continuous fixed effect for baseline NT-proBNP level (log-transformed) will be used to compare treatment groups. The method of handling missing NT-proBNP levels for this analysis is described in Section 7.3.

Comparisons between treatment groups regarding the binary endpoint variable (improvement in KCCQ-TSS of  $\geq 10$  points after 90 days of treatment) will be performed using a logistic regression model adjusting for the binary covariate HF status (de novo or decompensated chronic HF). The likelihood-ratio test will be used to test for a difference between treatments. Adjusted odds ratios together with 1-sided 97.5% confidence limits will be used to quantify the effect of treatment, comparing empagliflozin to placebo as the reference.

Time to event endpoints will be analysed using the Cox proportional hazards model [[R07-4680](#)] with HF status (de novo or decompensated chronic HF) as a covariate. Hazard ratios (HRs) and their associated one-sided 97.5% confidence limits will be estimated for evaluating the superiority of empagliflozin to placebo.

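### Does the 87.4% power fail because the KCCQ-TSS standard deviation is labelled baseline adjusted and no missing data are listed?

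*Protocol*

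**What the plan says.** Protocol section 7.5 estimates power by simulation. Deaths and heart failure events (HFEs) come from a shared gamma frailty. For KCCQ-TSS, "the frailty terms were directly transformed into a capped normal distribution", with a placebo mean of 55, an effect of 6, a win threshold of 5 and "KCCQ-TSS baseline adjusted standard deviation = 20". On these inputs 500 patients "would provide 87.4% power to detect a difference between the empagliflozin treatment group and placebo treatment group". Table 7.5: 1 varies the effect (4 to 7) and the hazard ratios. It does not vary the SD, and no missing share is listed.

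In the analysis itself, Protocol section 7.2.2 makes KCCQ-TSS the fourth tier of the win ratio, where "more positive change from baseline is better". SAP section 9.1.1 computes that change by plain subtraction. The only adjustment is the stratification by HF status.

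On gaps, Protocol section 7.3 states: "Missing data for KCCQ-TSS and NT-proBNP will be estimated using multiple imputation, according to whether patients are on-treatment or off-treatment". SAP sections 6.6.1 and 9.2 impute on-treatment gaps as missing at random and off-treatment gaps by jump-to-placebo, and they keep every observed off-treatment value. Protocol section 7.2.1 says of using all on- and off-treatment data: "This equates to a treatment-policy style estimand".

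**The concern.** The simulated quantity and the analysed quantity do not obviously match. Section 7.5 describes one capped score per patient and no baseline, yet labels the SD as baseline adjusted. Protocol section 7.2.3 uses a mixed model with baseline as a covariate "to obtain adjusted means for the treatment effects", so a reader may take the planning SD to be covariate-adjusted too. The SD of raw change would then be at least 20, because

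Var(change) = residual variance + (slope − 1)² × Var(baseline).

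The second worry is missing scores. Jump-to-placebo removes the drug effect from missing off-treatment scores in the empagliflozin arm. If 6 is an on-treatment effect, the analysed effect is smaller.

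Both matter because most pairs are settled on KCCQ-TSS. The stated power is the justification for 500 patients, and a reader cannot tell which cell of Table 7.5: 1 describes the planned analysis.

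**Working it through.** **1. Reproducing the plan's figure.** Inputs from Protocol section 7.5: 250 per arm, 90-day death 5%, at least one HFE 15% (both taken as placebo rates), hazard ratios 0.8 and 0.7, at most 7 HFEs, placebo mean 55, SD 20, effect 6, threshold 5, one-sided 0.025. The test was the log win ratio over its U-statistic standard error, in a single stratum. The frailty variance is not stated and was scanned:

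| Frailty variance | Power |
|---|---|
| 0.05 (10,000 trials) | 87.4% |
| 0.1 (20,000 trials) | 87.0% |
| 0.5 | about 84–85% |
| 1.0 | about 82–83% |

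At variance 0.1, with 10,000 trials per cell, all 12 cells of Table 7.5: 1 came within 1.1 points. The stated power is therefore right for its listed inputs if the frailty variance is small.

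**2. Weight of the KCCQ tier.** Ignoring frailty, the event-free proportions are:

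- placebo: 0.95 × 0.85 = 0.8075
- empagliflozin: 0.95^0.8 × 0.85^0.7 = 0.9598 × 0.8925 = 0.857

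Pairs reaching KCCQ-TSS: 0.8075 × 0.857 = 0.69. The simulation also gives 69%.

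**3. If 20 is covariate-adjusted.** Assume equal variances at baseline and Day 90 and correlation r. The adjusted SD is σ√(1 − r²) and the SD of change is σ√(2(1 − r)), so

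SD(change) = 20 × √(2/(1 + r)) = 21.7, 23.1, 24.8 for r = 0.7, 0.5, 0.3.

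The equivalent effect at SD 20 is 6 × 20/SD(change).

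**4. If 6 is an on-treatment effect.** With a share m of active-arm scores missing off-treatment, unrelated to events, the effect becomes 6 × (1 − m).

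**5. Reading power from the sponsor's own row** (hazard ratios 0.8 and 0.7: 63.6%, 77.2%, 87.4%, 93.4%), interpolated on the probit scale. Example for effect 5.20: Φ⁻¹(0.772) = 0.745 and Φ⁻¹(0.874) = 1.146, so 0.745 + 0.20 × 0.401 = 0.825 and Φ(0.825) = 79.5%.

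| Assumed case | Equivalent effect | Interpolated | Simulated, variance 0.1 | Simulated, variance 0.05 |
|---|---|---|---|---|
| As stated | 6 | 87.4% | 87.0% | 87.4% |
| SD 21.7 | 5.53 | 83.1% | 82.5% | 83.1% |
| SD 23.1 | 5.20 | 79.5% | 79.1% | 79.6% |
| SD 24.8 | 4.84 | 75.2% | 75.2% | 75.6% |
| 5% missing | 5.7 | 84.7% | 84.0% | not run |
| 10% missing | 5.4 | 81.7% | 81.0% | 81.5% |
| 20% missing | 4.8 | 74.7% | 74.3% | 75.7% |
| SD 23.1 and 10% missing | 4.68 | 73.1% | 73.3% | 74.1% |

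The interpolation is approximate, since the 5-point threshold and the 0–100 cap do not scale with the SD, but the simulations agree with it to about a point. Simple dilution also omits between-imputation variance. With a real imputation step (SD 23.1, 10% missing in both arms, 20 imputations) power was 72.5%, against 73.3% by dilution.

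**6. What the documents supply.** Every row below the first needs a correlation or a missing share that appears in neither document. The plan also limits such gaps. After a patient stops drug, "every effort should be made for the patient to attend the regularly scheduled study visits" (Protocol section 3.3.4.1), and section 10.5 lets KCCQ be completed at home during COVID-19 restrictions.

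**The case for a change.** The strongest case for acting is that the ambiguity runs one way. Raw change cannot have a smaller SD than the covariate-adjusted score, and jump-to-placebo can only dilute an on-treatment effect, so power stays at about 87% or falls. The protocol foresees patients whose events are known but whose KCCQ-TSS may be missing: section 3.3.4.1 allows phone visits and, in rare cases, only vital status and HFE information. A footnote in SAP section 6.6.1 counts everything after any treatment stop as off-treatment for imputation, although restarts are allowed. Re-running the simulation would be cheap.

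Much of this stands as a description. Section 7.5 leaves the SD label and the frailty variance undefined, and does not say whether 6 is net of discontinuation. It does not follow that the power is wrong. *Baseline adjusted* can equally mean adjusted by subtraction, which is the ranked quantity; the wording in section 7.2.3 concerns a secondary mixed model and does not define a planning input. Silence on missing data does not show that complete data were assumed. The sources cited for the SD and the effect would settle both questions, but they are not available here.

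The sensitivity is also largely visible already. On the scaling above, an SD of change of 24 (6 × 20/24 = 5) or 16.7% dilution (6 × 0.833 = 5) corresponds approximately to the published effect-5 cell, 77.2%. The effect-4 cell, 63.6%, is lower than any case in the table above.

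**Conclusion.** No change is needed. The 87.4% is correct for its stated inputs, given a frailty variance of about 0.05 to 0.1. If 20 is the SD of change and 6 is a treatment-policy effect, about 87% stands, apart from a small loss of information where scores are missing. On the less favourable readings either issue alone gives roughly 75% to 85%, and SD 23.1 with 10% missing gives 73% to 74%. Those figures rest on assumed correlations of 0.3 to 0.7, missing shares of 5% to 20% unrelated to events, and a small frailty variance. The size of any loss is therefore not established.

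What remains is missing detail in a planning calculation. Defining the inputs would help a reader, but it would leave the 500 patients, the win ratio, its imputation, the one-sided 0.025 test and the interpretation of the result as they are. Anyone who does explore missingness should consider every pair that reaches the KCCQ tier within its shared follow-up. Patients alive without an HFE are the only ones compared there when event follow-up is complete, and withdrawal of consent breaks that condition.

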## **8. INFORMED CONSENT, TRIAL RECORDS, DATA PROTECTION, PUBLICATION POLICY, AND ADMINISTRATIVE STRUCTURE**

The trial will be carried out in compliance with the protocol, the ethical principles laid down in the Declaration of Helsinki, in accordance with the ICH Harmonized Guideline for Good Clinical Practice (GCP), relevant BI Standard Operating Procedures (SOPs), the EU directive 2001/20/EC / EU regulation 536/2014 and other relevant regulations. Investigators and site staff must adhere to these principles. Deviation from the protocol, the principles of ICH GCP or applicable regulations as will be treated as “protocol deviation”.

Standard medical care (prophylactic, diagnostic and therapeutic procedures) remains the responsibility of the treating physician of the patient.

The investigator will inform the sponsor immediately of any urgent safety measures taken to protect the trial patients against any immediate hazard, as well as of any serious breaches of the protocol or of ICH GCP.

The Boehringer Ingelheim transparency and publication policy can be found on the following web page: [trials.boehringer-ingelheim.com](http://trials.boehringer-ingelheim.com). The rights of the investigator and of the sponsor with regard to publication of the results of this trial are described in the investigator contract. As a rule, no trial results should be published prior to finalisation of the Clinical Trial Report.

The certificate of insurance cover is made available to the investigator and the patients, and is stored in the ISF.

### **8.1 TRIAL APPROVAL, PATIENT INFORMATION, INFORMED CONSENT**

This trial will be initiated only after all required legal documentation has been reviewed and approved by the respective Institutional Review Board (IRB / Independent Ethics Committee (IEC and competent authority (CA) according to national and international regulations. The same applies for the implementation of changes introduced by amendments.

Prior to patient participation in the trial, written informed consent must be obtained from each patient (or the patient's legally accepted representative) according to ICH-GCP and to the regulatory and legal requirements of the participating country. Each signature must be personally dated by each signatory and the informed consent and any additional patient-information form retained by the investigator as part of the trial records. A signed copy of the informed consent and any additional patient information must be given to each patient or the patient's legally accepted representative.”

The patient must be given sufficient time to consider participation in the trial. The investigator or delegate obtains written consent of the patient's own free will with the informed consent form after confirming that the patient understands the contents. The investigator or his delegate must sign (or place a seal on) and date the informed consent form. If a trial collaborator has given a supplementary explanation, the trial collaborator also signs (or places a seal on) and dates the informed consent.

Re-consenting may become necessary when new relevant information becomes available and should be conducted according to the sponsor's instructions.

If study conduct may need to be adjusted (see [Sections 6.1](#) and [10.5](#)) during the COVID-19 pandemic, the patient must be made aware of any modifications and agreement needs to be obtained prior to them being implemented.

The consent and re-consenting process should be properly documented in the source documentation.

